### 9.4 Association analysis of trans-impedance and intra-cochlear voltage measurements with the NRT thresholds and intra-cochlear electrode array position over time

The intra-cochlear electrode position properties will be correlated against the trans-impedance and voltage measurements as well as the NRT thresholds using pairwise Pearson product-moment correlation coefficient.

For each implanted ear the trans-impedance and voltage measurements as well as the NRT thresholds will be compared across the three measurement times (intra-operative, first activation and 3 months) to determine the stability. Any changes in one of the measurements will be compared with the others to check for co-variance.

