2.1 Overview

A total of 154 patients will be assessed in the statistical analysis of the data. This will serve to collect a representative sample of the variability of surgical techniques across clinics and surgeons. The confidence interval to be used in the analyses will be a 90% two-tailed. This confidence interval was deemed to be satisfactory due to the exploratory nature of the study. The statistical analyses conducted for the primary and secondary objectives will lead to the endpoints of the study.

The statistical analysis will be conducted by [REDACTED], Cochlear).

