The second secondary object of this study is to investigate the changes in the trans-impedance, intra-cochlear voltage and the NRT thresholds over time to identify the stability of the measurements. The contact points for the patients in the study are surgery, activation (4

weeks after surgery) and 3 months post-operative. Investigating how the measurements change throughout time will involve:

- Excluding patients that have been confirmed (by imaging) to have an anomalous position.
- Characterising the measurements at each contact point
- Characterising the changes in measurements between the contact points

Characterising the measurements at each contact point involves:

- Visualising the distributions (e.g. scatter plots, frequency histograms, boxplots, etc.)
- Calculating the distribution statistics (e.g. normality, mean, median, standard deviation, confidence intervals around mean and medians)
- Parametric or non-parametric ANOVA between the distributions of each contact point

Characterising the changes in measurements between the contact points involves:

- For each patient calculating the difference between the measurements at each time point to create difference distributions
- Visualising the difference distributions (e.g. scatter plots, frequency histograms, boxplots, etc.)
- Calculating the distribution statistics (e.g. normality, mean, median, standard deviation, confidence intervals around mean and medians)

A parametric or non-parametric (Friedman) ANOVA will be conducted on the difference distributions of the periods between each contact point to establish the significance of the time factor.

This information will provide guidance on the time from surgery during which the findings of candidate algorithms can be considered valid.

3.4 Secondary objective 3

To ensure the correct handling and storage of patient data for the study, study measurements and metadata will be uploaded to a clinical study database. The database will be structure accordingly:

- A section storing patient information such as:
 - Identifier
 - Implant
 - Demographics
 - Medical history
 - Adverse events
 - Medical professionals' notes and comments
 - Surgical variables
 - Nature of insertion

- A section storing CT images, the operating medical professionals notes and electrode positioning
- A section storing trans-impedance measurements, the measurement parameters and the point in time the measurement was taken

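### The test that SAP 3.3 designates for the time factor compares the changes with one another, so it can miss steady drift that the planned intervals show

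*SAP*

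**What the plan says.** SAP 3.3 covers changes in trans-impedance, intra-cochlear voltage and NRT thresholds over three contact points: surgery, activation at 4 weeks, and 3 months. Patients with a confirmed anomalous position are left out. The section plans three things:

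- At each contact point, descriptive statistics and a "Parametric or non-parametric ANOVA between the distributions of each contact point". It does not say whether this is paired.
- "For each patient calculating the difference between the measurements at each time point to create difference distributions", with descriptive statistics that include "confidence intervals around mean and medians". SAP 2.1 sets the level: "The confidence interval to be used in the analyses will be a 90% two-tailed".
- A parametric or Friedman "ANOVA will be conducted on the difference distributions of the periods between each contact point to establish the significance of the time factor".

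Only the third is given the job of deciding whether time matters. The section then states the use: "This information will provide guidance on the time from surgery during which the findings of candidate algorithms can be considered valid". Protocol 9.4 names no test, but says that the trans-impedance and voltage measurements and the "NRT thresholds will be compared across the three measurement times (intra-operative, first activation and 3 months) to determine the stability".

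**The concern.** Differencing already removes the visit level, so an ANOVA across difference distributions tests whether one change is as large as another. If a measurement rises by the same amount in both periods, the two changes are equal and the test has nothing to find, although the measurement is plainly not stable.

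The result also depends on choices that the SAP leaves open: two or three differences, and their signs. A report could therefore carry a non-significant time factor beside an interval for change that excludes zero, with no rule on which to believe, in the section that is meant to inform how long after surgery algorithm findings hold.

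**Working it through.** **Inputs.** SAP 3.3 gives no effect size, SD or power, so there is no figure of its own to reproduce. From the SAP: n = 154 − 9 = 145 normal insertions (2.2), two-sided level 0.10 (2.1), three contact points (3.3). Assumed, because the documents give none: normal values, between-patient SD 1, residual SD σ = 0.5, and drifts stated in units of σ.

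**What each reading tests.** Let d1 = activation − surgery, d2 = 3 months − activation, d3 = 3 months − surgery = d1 + d2, and let μ denote means.

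- *Two consecutive differences.* The null is μ1 = μ2. It holds for any equal step. This reading is open for the parametric option; SciPy's Friedman function refuses fewer than three samples.
- *Three forward differences.* The null is μ1 = μ2 = μ1 + μ2, which forces μ1 = μ2 = 0. The question is right, but the three are linearly dependent and an equal step δ gives means δ, δ, 2δ, of which only the spread counts.
- *Three differences with cyclic signs (d1, d2, −d3).* These sum to zero, so equal means again imply no change.

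**Worked example.** Let both mean changes be 0.30 with SD of change 1. Each 90% interval is 0.30 ± 1.656 × 1/√145 = 0.30 ± 0.14, or 0.16 to 0.44. Both exclude zero. The two means are equal, so F = 0 and p = 1.

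**Power by formula.** d2 − d1 has SD √6 σ, so its standard error is 2.449σ/12.04 = 0.203σ. d3 has SD √2 σ and standard error 0.117σ.

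- Equal steps of 0.25σ: the mean of d2 − d1 is 0, so the two-difference test rejects in 10%. d3 has mean 0.5σ and 0.5/0.117 = 4.26, so its 90% interval excludes zero in 99.5%.
- Drift linear over weeks 0, 4 and 13, total 0.5σ: the steps are 0.154σ and 0.346σ, and 0.192/0.203 = 0.95 gives about 25%.
- Change of 0.5σ before activation, then none: 0.5/0.203 = 2.46 gives 79%. A rise of 0.25σ with full return has the same d2 − d1 in size, so also 79%.

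**Simulation** (4,000 to 10,000 runs per row; rejection at the 10% level, in %; paired entries are Friedman / repeated-measures ANOVA):

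| Change, in σ | Three visit values | Three forward differences | Two consecutive differences, paired test |
|---|---|---|---|
| None | 10.0 / 9.6 | 10.5 / 11.5 | 9.6 |
| 0.25 in each period | 95 / 99 | 63 / 56 | 10 |
| 0.5 in each period | 100 / 100 | at least 99.8 | 10 |
| Linear in weeks, total 0.5 | 95 / 99 | 69 / 68 | 24 |
| 0.5 early, then plateau | 98 / 99.7 | 91 / 95 | 79 |
| Rise of 0.25, full return | 57 / 71 | 68 / 82 | 79 |

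Three cyclic differences match the visit values (95 / 99 at 0.25 per period). With a Greenhouse-Geisser correction, the repeated-measures ANOVA on three forward differences falls from 56% to 46% at 0.25, and its type I error from 11.5% to 9.3%.

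**How often the outputs disagree** (surgery-to-3-month interval excludes zero, designated test not significant). With two consecutive differences: about 90% of runs at equal steps of 0.25, 0.5 and 1.0, 75% for drift linear in weeks, and 9% with no drift. With three forward differences: 37% (Friedman) to 44% (repeated-measures ANOVA) at 0.25, 3% to 5% at 0.375, and about 0% at 0.5.

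**The visit-level ANOVA.** If run unpaired, its power at 0.25 per period is 34%. It depends on the assumed between-patient SD: 91% at 0.5 and 1% at 1.5.

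**The case against.** The strongest reply is that three pairwise differences were probably meant. The SAP names Friedman and SciPy, which needs three samples, and it forms differences between time points without restricting them to neighbours. The null is then no mean change, and what remains is lower power against small drift, gone by 0.5σ per period. This stands for that reading. But the sentence speaks of the periods between contact points, of which there are two, and the parametric option needs no third sample.

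Second, equal steps are the worst case for two differences. The periods are about 4 and 9 weeks, so equal steps need the weekly rate to roughly halve, and Protocol 5 expects tissue encapsulation in the first months, which suggests early change and then a plateau. That is fair, and the loss there is smaller (79% against 98% or more at 0.5σ). For rise and return, the SAP's test does better than one on visit values.

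Third, the same section plans intervals for each difference and a visit-level ANOVA, and Protocol 8.1 and 9.2 evaluate specificity at each visit directly. So drift would usually be seen, and the period of validity does not rest on this p-value alone. This also stands, with two limits: an unpaired visit-level ANOVA can be weak, and checks of specificity say nothing about NRT thresholds, which belong to this objective.

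None of this removes the fault: the conclusion about time is attached to the output least suited to give it, with no rule for disagreement.

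**Conclusion.** The concern holds. On the two-period reading, the designated test addresses the wrong question and cannot detect equal change in both periods, whatever its size. On the three-forward-difference reading, it addresses the right question with less power against small drift (56% to 63% against 95% to 99% at 0.25σ per period) and is slightly liberal without correction. With cyclic signs nothing material is lost, but the SAP does not specify them.

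The algebra needs no assumption. The percentages rest on the assumed normal model, the SDs and the drift patterns, with n = 145. SAP 3.3 as a whole need not miss drift. The objective is secondary and exploratory; the primary specificity analysis and N = 154 are unaffected. It should be corrected before analysis, but it does not threaten the trial's main result.

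**What to change.** In SAP 3.3:

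1. Take the time-factor test from the three visit values, within patient: repeated-measures ANOVA, Friedman, or a mixed model with visit as a fixed effect and a random patient effect. This agrees with Protocol 9.4. The mixed model keeps patients who miss a visit, as SAP 4 intends; Friedman drops them.
2. Run the listed visit-level ANOVA as paired, or let the test in step 1 replace it.
3. Keep the difference distributions for estimation. List which differences are formed and with what sign, and read their 90% intervals against zero.

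The cost is SAP wording and standard software; no new data are needed. The downside is somewhat lower power for a pure rise and return. The consecutive-difference intervals cover that pattern: at a rise of 0.25σ at least one excludes zero in 83% of runs, although these intervals are unadjusted and at least one does so in 17% with no drift.

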Appendix A

```
# -*- coding: utf-8 -*-
```

```
"""
```

```
Created on Fri May 13 14:21:16 2016
```

```
"""
```

```
# Script was run using Ananconda Scientific Python 2.7 64 bit
```

```
# https://www.continuum.io/downloads
```

```
# This script is used to:
```

```
# i) Calculate the perimodiolar weighted average tip fold-over rate between
```

```
# Zuniga et al. (2017) and Grolman et al. (2009).
```

```
# ii) For a given sample size, estimate the number of tip fold-overs for a
```

```
# binomial cumulative percentage equivalent to 90%.
```

```
# iii) With a given sample size minus the number of tip-fold-overs estimated,
```

```
# estimated the lower bound of the 90% binomial confidence interval when the
```

```
# the probability is equal to 100%. This lower bound value must be equivalent
```

```
# to the target specificity of 98%.
```

```
# iv) Calculate the postivite predivtive value with a target specificity of 98%
```

```
# and target sensitivity of 90%.
```

```
# Notes:
```

```
# Assuming a 90% confidence interval
```

```
# copy.deepcopy() is used to mitigate Python's memory management protocols.
```

```
# Import anaconda/python libraries
import numpy as np
import scipy.stats as sp
import copy

# Defining functions
# Clopper-Pearson exact binomial confidence interval
# Clopper, C. J., & Pearson, E. S. (1934). The use of confidence or fiducial
# limits illustrated in the case of the binomial. Biometrika, 26(4), 404-413.
# Method detailed on page 407 of Clopper & Pearson (1934).
def two_tailed_exact_binomial_CI(p,n,x,alpha,fidelity):
    # p: recorded probability of success
    # n: number of trials performed
    # x: recorded number of successes
    # alpha: confidence interval
    # fidelity: number of probability steps (step size indication) for runs 0
    # to p (lower bound) and from p to 1 (upper bound)

    # Two-tailed
    alpha_2 = alpha/float(2)

    # Finding upper bound probability
    p_upper = 1
```

```
for k in np.linspace(p,1,fidelity):
    # Resetting summate
    summate = 0

    # Select probability
    input_prob = copy.deepcopy(k)

    # Calculating sum loop
    for m in np.arange(x+1):
        summate = summate + sp.binom.pmf(m, n, input_prob)

    # Determining
    if summate < (alpha_2+0.0020) and summate > (alpha_2-0.0020):
        p_upper = input_prob

# Finding lower bound probability
p_lower = 0
for k in np.linspace(0,p,fidelity):
    # Resetting summate
    summate = 0

    # Select probability
    input_prob = copy.deepcopy(k)

    # Calculating sum loop
    for m in np.arange(x,n+1):
        summate = summate + sp.binom.pmf(m, n, input_prob)

    # Determining
    if summate < (alpha_2+0.0020) and summate > (alpha_2-0.0020):
        p_lower = input_prob

# Returning
return [p_lower,p_upper]
```

```
# Main program
if __name__ == '__main__':
    # Selecting sample size for analysis
    n = 154

    # PART (i)
    # Calculating weighted average between the two papers
    # Zuniga et al. (2017) - 5 tip fold-overs out of 0.48*303 perimodiolar
    # electrode arrays
    p_z = 5 / (0.48 * 303)
    # Grolman et al. (2009) - 4 tip fold-overs out of 72 perimodiolar electrode
    # arrays
    p_g = 4 / float(72)
    # Weighted tip fold-over rate
    p_w = ((0.48 * 303)*p_z + (72)*p_g)/float((0.48 * 303)+72)

    # Prior rate of tip fold-over - Using the weighted tip fold-over rate
    p_ETF = copy.deepcopy(p_w)

    # PART (ii)
    # Calculating the binomial probability mass distribution up to and including
    # 15 tip fold-overs
    max_ETF = 15
    record_n_ETF = np.zeros(max_ETF+1)
    record_p_n_ETF = np.zeros(max_ETF+1)
    for k in np.arange(0,max_ETF+1):
        # Number of tip foldovers
        n_ETF = k
```

```

# Estimating probability of n ETF
p_n ETF = sp.binom.pmf(n ETF, n, p ETF)

# Updating
record_n ETF[k] = n ETF
record_p_n ETF[k] = p_n ETF

# Integrating the binomial probability mass function and finding the number
# of tip fold-overs at a cumulative probability equivalent to 90%.
# Expected number of tip fold-overs
expectation = np.ceil(n*p ETF)
# Variables to contain results
max_n ETF_single = 0
max_n ETF_single_cumulative = 0
# Variable to contain integral
summation = 0
# Integrating
for k in np.arange(len(record_n ETF)):
    # Recording cumulative percentage
    summation = summation + record_p_n ETF[k]
    # Determining if the cumulative percentage (summation) is equivalent to
    # 90%.
    if summation<=(0.90+0.03) and summation>=(0.90-0.03) and
record_n ETF[k]>=expectation:
        # Recording number of tip fold-overs
        max_n ETF_single = record_n ETF[k]
        max_n ETF_single_cumulative = copy.deepcopy(summation)

# Finding new sample size
n_new = n - max_n ETF_single
print('Cumulative percentage')
print(max_n ETF_single_cumulative)
print('Resultant sample size')
print(n_new)

# PART (iii)

```

```
# Calculating confidence interval for true negative rate of 100% of
hypothetical
# algorithm given n_new using the Clopper-Pearson exact method.
# Probability
p = 1
# Recorded number of successes
x = copy.deepcopy(n_new)
# 1 - confidence interval
alpha = 0.10
# Search fidelity - increases the number of probabilities that are analysed
fidelity = 8000
# Clopper-Pearson function
output = two_tailed_exact_binomial_CI(p,n_new,x,alpha,fidelity)
p_lower = output[0]
p_upper = output[1]
del(output)
print('Lower bound of binomial confidence interval')
print(p_lower)

# PART (iv)
# Positive predictive value
# PPV = (prevalence * sensitivity) / ((prevalence*sensitivity)+((1-
specificity)*(1-prevalence)))
sensitivity = 0.90
specificity = 0.98
prevalence = p_w
PPV = (prevalence*sensitivity) / ((prevalence*sensitivity)+((1-
specificity)*(1-prevalence)))
print('Positive predictive value')
print(PPV)
```
